We hypothesize that Myrbetriq™, as a $\beta(3)$ -AR agonist⁶, could harbor a great therapeutic potential for controlling storage bladder symptoms (LUTS) and ureteral pain associated with ureteral stent placement.

Study Objective and Endpoints

The objective of this pilot study is to assess whether Myrbetriq™ will improve post-operative ureteral pain and discomfort, reduce bladder storage symptoms and increase quality of life following ureteral stenting. This study will be conducted as an exploratory pilot investigation. In doing so, we will confirm the potential effect size for reduction in associated pain following stenting within this study population. Results from this pilot study will also be used to assess feasibility for the design and conduct of a larger, prospective study in this population.

Primary Endpoints:

- Improvement from baseline in the Incontinence Symptom Severity Index (ISSI) in the Myrbetriq™ group at the 1 week follow-up and 2 week follow-up compared to placebo group.
- Improvement from baseline in the number micturition per 24 hours and the number of incontinence episodes in the Myrbetriq™ group at the 1 week follow-up and 2 week follow-up compared to placebo group.

Exploratory Endpoints:

- Improvement in pain and discomfort perception using a 10 point Visual Analog Scale for pain assessment (VAS) at the 1 and 2 week follow-up.
- Improvement from baseline on the Patient Global Impression of Severity (PGI-S) at the 2 week follow-up.

- Reduction in pain medicine intake at the 2 week follow-up.

Study Methods

This study is a prospective, randomized, double-blind, placebo-controlled 2 week clinical trial to evaluate the efficacy of Myrbetriq™ to reduce ureteral stent related pain and bladder symptoms in subjects undergoing a urologic procedure involving ureteral stenting. The study will be conducted at Southern Illinois University (SIU) School of Medicine, Department of Urology and its affiliated hospitals in Springfield, IL.

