Data analysis will be concluded upon the completion of the study. Subjects' age, height, weight, and other continuous baseline variables will be summarized using descriptive statistics, while gender, race and other categorical variables will be provided using frequency tabulations. Medical history data will be summarized using frequency tabulations by system organ class and preferred term. Chi-square and t-tests will be used, as appropriate, to compare percent change and mean change from baseline in the ISSI, voiding diary, narcotic log, VAS score and PGI-S at the final study visit (14 days) or at any early termination visit. A split-plot ANOVA with repeated measures will be used for each measure (ISSI, VAS and PGI-S) to compare groups (Myrbetriq™ and placebo) over time and to determine if there is an interaction between groups. Significance will be assumed when $p < 0.05$. A preliminary power analysis based on previously published data, using an estimated SD for each study group of 4.17, a sample size of 50 in each study group (Myrbetriq™ and placebo) has an 80% power to detect an ISSI difference of 25% between the two groups with a significance level (alpha) of 0.05 (two-tailed)¹².

Pertinent to each Specific Aim are the following calculations:

- Primary Endpoints: Comparison of the change from baseline in ISSI and voiding diaries between Myrbetriq™ and placebo will be made using an independent t test for continuous scoring and a chi-squared test for ordinal scoring. Inferential analyses of changes from base line in micturition episodes per 24 hours and incontinence episodes per 24 hours will be performed using a stratified rank analysis to compare to baseline and as a covariance for each treatment.
- Exploratory Endpoints: Comparison of the change from baseline of total VAS between Myrbetriq™ and placebo will be made using an independent t test for continuous scoring and a chi-squared test for ordinal scoring. Comparison of the change from baseline in PGI-S between Myrbetriq™ and placebo will be made using an independent t test for

continuous scoring and a chi-squared test for ordinal scoring. Comparison of pain medicine intake between Myrbetriq™ and placebo groups will be made using an independent t test.

Safety Considerations

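### Two of the three primary measures are analysed as change from a diary baseline recorded only after treatment has started; as a lesser point, no primary comparison is named as deciding

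*Combined protocol and SAP*

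**What the plan says.** **Endpoints.** Study Objective and Endpoints lists two primary items: "Improvement from baseline in the Incontinence Symptom Severity Index (ISSI) in the Myrbetriq™ group at the 1 week follow-up and 2 week follow-up" and "Improvement from baseline in the number micturition per 24 hours and the number of incontinence episodes", the second at the same two follow-ups. That is three measures at two visits. The same section states: "This study will be conducted as an exploratory pilot investigation".

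**Diary timing.** One sentence in Study Methods opens by saying that all instruments are completed at baseline and at every follow-up. Its diary item then sets its own times: the 1 to 3 days before day 7, before the stent removal visit, and 14 days after removal provided removal is done by day 28. It gives obtaining the baseline diary as the purpose of that last record. Study drug starts on the day of stent placement. In the schedule of assessments, ISSI, VAS, PGI-S and AUASS are marked at Baseline/Stent Placement and the voiding diary is not. The diary is marked at day 7, at stent removal (or day 14), and at the post-removal contact, for which day 42 is the alternative.

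**Analysis.** Statistical Analyses plans chi-square and t-tests "to compare percent change and mean change from baseline in the ISSI, voiding diary, narcotic log, VAS score and PGI-S". The time point it sets for these tests is "at the final study visit (14 days) or at any early termination visit". It adds, for ISSI among others: "A split-plot ANOVA with repeated measures will be used for each measure (ISSI, VAS and PGI-S) to compare groups". The diary counts also get a stratified rank analysis with no strata named. The threshold is "Significance will be assumed when $p < 0.05". The only power statement concerns ISSI: 50 per group with an SD of 4.17 "has an 80% power to detect an ISSI difference of 25% between the two groups".

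**The concern.** A change from baseline is a fair between-arm measure because the baseline is fixed before treatment can touch it. Here the record that serves as baseline for both diary measures is taken after randomisation, after dosing has begun and after the stent is out. It is an outcome, and using it as the subtrahend changes what is estimated. Whether a patient has the record may also depend on when the stent came out, which is itself a post-randomisation event. Two of the three primary measures are affected. ISSI is not, because it has a baseline mark at placement.

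Separately, a reader of the results could not tell from the plan which primary comparison carries the conclusion. The endpoint section and the analysis section imply different numbers of comparisons, and each comparison would be declared significant at the same threshold.

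**Working it through.** **1. The diary baseline**

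| Place | What it gives for the diary |
|---|---|
| Study Objective and Endpoints | Improvement from baseline, weeks 1 and 2 |
| Statistical Analyses | Change from baseline, compared between arms |
| Study Methods, opening of the sentence | Completed at baseline |
| Study Methods, diary item | Every listed time follows placement; the baseline record comes 14 days after removal, if removal is by day 28 |
| Schedule of assessments | No mark at Baseline/Stent Placement; last mark at the post-removal contact or day 42 |

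The specific diary times and the schedule agree that no diary precedes treatment. Only the general opening phrase points the other way.

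*Timing.* Removal on day 14 puts the reference diary at 14 + 14 = day 28. Removal on day 28 puts it at 28 + 14 = day 42. Dosing is stated as up to 4 weeks (28 days). The documents do not say whether dosing ends at an earlier removal, and the drug accountability row has a conditional entry at the post-removal contact. So they do not establish that the reference record is free of study drug.

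*Effect on the estimate.* Let θ be the treatment effect on the on-treatment rate and φ any treatment effect still present in the reference record. The between-arm difference in change estimates θ − φ. It equals θ only if φ = 0. Nothing in the documents gives φ.

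*Precision.* With equal variance σ² and correlation ρ between the two records, the change has variance 2σ²(1 − ρ). This is below σ² only when ρ > 0.5. The documents give no ρ, so subtraction is not assured of gaining precision.

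**2. The number of primary comparisons**

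*The plan's own figure.* Inputs from Statistical Analyses: SD 4.17, 50 per group, two-sided 0.05, 80% power. By the normal approximation the detectable difference is (1.960 + 0.842) × 4.17 × √(2/50) = 2.34 points. If this is 25%, the reference mean is 2.34/0.25, about 9.35. That mean is not stated, so the 80% cannot be confirmed. With a mean of 8 the power would be 67%, and with a mean of 10 it would be 85%. Whatever the true figure, ISSI is the only measure with a power statement.

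*Count.* Endpoints: 3 measures × 2 visits = 6. Tests dated to day 14: 3 × 1 = 3.

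*Chance of at least one p < 0.05 if the drug has no effect, with one test per comparison.* For independent comparisons, two-sided: 1 − 0.95³ = 14.3% and 1 − 0.95⁶ = 26.5%. In the drug's favour: 1 − 0.975³ = 7.3% and 1 − 0.975⁶ = 14.1%. For equally correlated normal statistics with correlation r and c = 1.96:

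1 − ∫ φ(u) [Φ((c − √r·u)/√(1−r)) − Φ((−c − √r·u)/√(1−r))]ᵏ du,

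where φ(u) is here the standard normal density. The second Φ is dropped for the drug's favour. The documents give no correlations, so r is assumed.

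| r (assumed) | Three: two-sided / favouring drug | Six: two-sided / favouring drug |
|---|---|---|
| 0 | 14.3% / 7.3% | 26.5% / 14.1% |
| 0.5 | 12.5% / 6.3% | 20.7% / 10.4% |
| 0.9 | 8.4% / 4.2% | 10.8% / 5.4% |

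One named comparison gives 5% / 2.5%.

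**The case against.** *On the diary.* The post-removal record may be meant as a stent-free reference for each patient, and if no drug effect remains two weeks after removal, φ is zero and the difference in change is unbiased. That is fair: no residual effect is shown or sized in the documents. What stands is that the plan calls the record a baseline, relies on φ = 0 without saying so, and does not secure it. The opening phrase in Study Methods and some garbled punctuation before day 7 might hint at a lost earlier diary, but the schedule, which is explicit, has none.

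A reader might also infer that patients without the diary by day 28 drop out of the analysis. The documents do not say that. Day 28 limits stent removal, not the diary, and removal on day 28 gives a diary on day 42. The schedule's day-42 alternative may cover later removals too, in conflict with the condition in Study Methods. How many patients would lack the record is unknown.

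*On multiplicity.* This is an exploratory pilot, mainly descriptive, with no decision attached to any p-value, so strict error control is not evidently needed. That largely stands and makes this part minor. A reader might infer a false-positive rate of about 26% for the trial. The documents do not support that. It needs a rule that any one significant result is success, which they do not state; it needs zero correlation, which is implausible for ISSI at two visits measured against the same baseline; and it counts results against the drug, although the endpoints concern improvement. If all comparisons had to succeed, the error would be at most 5%. What remains is that the plan still sets a threshold, plans inferential analyses and claims power, without saying which comparison they serve.

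**Conclusion.** The diary analysis is wrong as written and should be corrected before the data are analysed. Two of three primary measures are defined by change from a baseline that no section schedules before treatment, and the record named as that baseline is post-randomisation. The direction and size of any distortion are unknown; the conclusion rests on the timing alone, not on evidence of a residual effect.

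The absence of a deciding comparison is a low-severity matter. Under an any-one-succeeds reading, with one test per comparison and assumed correlations from 0.9 to 0, the false-positive chance in the drug's favour is 4.2–7.3% for three comparisons or 5.4–14.1% for six (two-sided 8.4–14.3% or 10.8–26.5%). These figures show what the ambiguity could allow. They are not an error rate that the plan commits to.

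**What to change.** **Diary.**
- Reconcile Study Objective and Endpoints, Study Methods, the schedule of assessments and Statistical Analyses on when the diary is kept, including the day-28 condition against the day-42 mark, and on which record counts as week 2 when removal falls on another day.
- Reword the two diary endpoints and their analysis together, as between-arm comparisons of on-treatment rates per 24 hours at week 1 and week 2 with no baseline subtraction. Changing only the analysis would leave it at odds with the endpoint.
- Keep one stated method, for example a rank-sum test, or a negative binomial model with diary days as offset, since diaries run 1 to 3 days.
- Report the post-removal diary descriptively under its own name.

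Cost: no new data, but no within-patient adjustment for the counts. A diary kept before placement would restore that adjustment, but it needs new collection and cannot serve patients already treated.

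**Deciding comparison.**
- Name the between-arm difference in week-2 ISSI mean change, by independent t-test, as the single comparison judged at two-sided 0.05, because ISSI alone has a power statement. The sponsor should confirm the choice: by its title, the cited ISSI validation is in women, while the trial enrols both sexes.
- Report the other primary comparisons with 95% confidence intervals and p-values labelled nominal.
- Make the split-plot ANOVA supportive.

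Cost: the other primary measures can no longer be declared significant.

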Subjects will be enrolled per the inclusion/exclusion criteria. Subjects will be screened and consented prior to their stent placement procedure for stone disease. Patients will be formally enrolled and randomized post-operatively based on no severe complications intra-operatively, such as extensive extravasation, hematoma could confound the pain and compromise the results. All subjects will complete at baseline and all follow-up visits: 1) the Incontinence Symptoms Severity Index (ISSI), 2) American Urologic Association symptom score (AUASS) 3) the Visual Analog Scale (VAS) to represent change in acute pain 4) the Patient Global Impression of Severity (PGI-S) quality of life scale 5) a voiding diary for 1 to 3 days preceding day, 7, and stent removal visits, and then 14 days after the stent removal (if done by day 28) to obtain base line diary and 6) a narcotic log starting after surgery through 14 days after stent removal (if done by day 28). The ISSI will be used to assess any change in voiding symptoms. This scale has been validated to efficiently capture and quantify urological symptoms⁷. The voiding diary is used to capture the number of micturition per day, urgency and associated incontinence. The VAS has been validated to measure changes in acute pain that are clinically significant⁸. The PGI-S has been proven to efficiently summarize a patient's perception to change in severity in regards to lower urinary tract symptoms (LUTS)⁹. Subjects will undergo a blood draw prior to stent placement (complete blood count (CBC), comprehensive metabolic panel (CMP) and urine analysis (sugar, protein, WBC/RBC, bacteria)) to verify eligibility. These laboratories will not be repeated if they were performed routinely as a part of preoperative work up. 100 subjects will be equally randomized into 1 of 2 study groups, active treatment with Myrbetriq™ or administration of a placebo. A daily 50 mg dose of Myrbetriq™ will be administered in the treatment group for up to 4 weeks initiated on the day of stent placement. A 50mg dose was chosen as the initial dose due to the acute nature of the symptoms which do not require long term therapy. It has been shown that Myrbetriq™ 50 mg taken orally once daily has superior efficacy in treatment of LUTS when compared to placebo by week 4 (the duration of this study) and this effect was maintained. A 50mg dose was proven to be safe and effective to patients in Phase III trials^{10,11}. Both study groups will receive similar prescriptions of narcotics in dose and number. Patients will be given a log to record use of narcotics. If a different form of narcotics is prescribed due to side effects or allergic reaction, a narcotic analgesia converter calculator will be used to adjust for the doses, for analysis purposes. Post-operative symptoms and pain medicine intake will be assessed at days 1, 7 via telephone interview, and with a clinic visit the day of stent removal (or day 14 if stent removal postponed) and via phone 14 days after the stent is removed. If patient is to have stent removed on day 28, or later, the patient will receive a day 21 telephone call to obtain post-operative pain and pain medicine intake, as well as questionnaires. They will remain on study drug until day 28. Use of prescription, over-the-counter and supplemental medications for pain control will be captured using self-report and direct observation/recording of medication labels by the study team. These interviews will be conducted by study staff who will be blinded to the subject's treatment. Subjects will complete

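### ISSI and VAS are compared by a t test on change from baseline; adjusting for the baseline already collected would be at least as precise at almost no cost

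*Combined protocol and SAP*

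**What the plan says.** The Statistical Analyses section gives the primary comparison of ISSI as follows: "Comparison of the change from baseline in ISSI and voiding diaries between Myrbetriq™ and placebo will be made using an independent t test" (a chi-squared test applies if scoring is ordinal). For the exploratory pain endpoint it says: "Comparison of the change from baseline of total VAS between Myrbetriq™ and placebo will be made using an independent t test". A more general sentence in the same section has chi-square and t tests used "to compare percent change and mean change from baseline in the ISSI, voiding diary, narcotic log, VAS score and PGI-S". It then adds: "A split-plot ANOVA with repeated measures will be used for each measure (ISSI, VAS and PGI-S) to compare groups". None of these names baseline as a covariate. The only covariance wording is in the analysis of micturition and incontinence episodes, which "will be performed using a stratified rank analysis to compare to baseline and as a covariance for each treatment". That sentence does not reach ISSI or VAS.

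Both scores are available at baseline. Study Methods says "All subjects will complete at baseline and all follow-up visits: 1) the Incontinence Symptoms Severity Index (ISSI", with VAS third in the same list, and the assessment schedule marks both at the Baseline/Stent Placement visit.

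The power statement is for ISSI only, "using an estimated SD for each study group of 4.17, a sample size of 50 in each study group", with 80% power for a 25% difference at two-sided alpha 0.05. It does not say whether 4.17 is the SD of a single score or of a change, or what the 25% is a percentage of. It gives no correlation between baseline and follow-up, and no SD for VAS.

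**The concern.** A t test on change subtracts the whole baseline score from the follow-up score. That is optimal only when the regression slope of follow-up on baseline is 1. With any other slope, the subtraction leaves avoidable baseline noise in the comparison. ANCOVA estimates the slope from the data.

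This matters because ISSI is a primary endpoint, with a stated power and a p < 0.05 criterion. It also matters because the objectives say of pain that "we will confirm the potential effect size for reduction in associated pain following stenting within this study population", as input to a larger study. The interval around an effect size is therefore a main product of this pilot, and it may be wider than the collected data require.

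There is a side issue. If percent change means each subject's own percentage change, it is undefined for anyone with a baseline score of 0.

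The voiding diary is outside this point, because the schedule shows no diary at the baseline visit.

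**Working it through.** **Inputs from the documents (Statistical Analyses):** 50 per arm, SD 4.17, two-sided alpha 0.05, power 80%. **Not in the documents, so assumed over a range:** the baseline-to-follow-up correlation ρ, and k = s0/s1, the ratio of baseline SD to follow-up SD.

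**1. The plan's own figure.** The 25% has no reference mean, so the 80% can only be inverted. By the normal approximation the detectable difference is 4.17 × √(2/50) × (1.960 + 0.842) = 4.17 × 0.2 × 2.802 = 2.34 points. By the noncentral t with 98 df it is 2.36. This is 25% of a mean of about 2.36/0.25 = 9.4, which the documents do not state. The 80% is therefore neither confirmed nor refuted. The 2.36 points serve below only as a common yardstick.

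**2. Variance of the two analyses.**
- Change score: s0² + s1² − 2ρ·s0·s1
- ANCOVA: (1 − ρ²)·s1²
- Difference: (s0 − ρ·s1)², which is never negative and is zero only when s0 = ρ·s1
- Ratio, change score to ANCOVA: (1 + k² − 2ρk)/(1 − ρ²), which is 2/(1 + ρ) at k = 1

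| k | ρ = 0.2 | ρ = 0.3 | ρ = 0.5 | ρ = 0.7 |
|---|---|---|---|---|
| 0.5 | 1.09 | 1.04 | 1.00 | 1.08 |
| 1 | 1.67 | 1.54 | 1.33 | 1.18 |
| 1.25 | 2.15 | 1.99 | 1.75 | 1.59 |

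At k = 1 and ρ = 0.9 the ratio is 1.05. These ratios do not depend on the scale, so they apply to VAS as well as ISSI.

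**3. ISSI power if 4.17 is the SD of change** (noncentral t; 98 df for the t test, 97 for ANCOVA). The t test has 80% power at 2.36 points, and its 95% CI half-width is 1.984 × 4.17 × 0.2 = 1.66 points. For ANCOVA the SD is 4.17/√ratio.

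| k | ρ | ANCOVA power | ANCOVA half-width |
|---|---|---|---|
| 1 | 0.3 | 93.5% | 1.33 |
| 1 | 0.5 | 89.9% | 1.43 |
| 1 | 0.7 | 86.0% | 1.53 |
| 1 | 0.9 | 82.0% | 1.61 |
| 0.5 | 0.3 | 81.7% | 1.62 |
| 0.5 | 0.5 | 80.0% | 1.66 |
| 0.5 | 0.7 | 82.9% | 1.59 |

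**4. ISSI power if 4.17 is the SD of a single follow-up score** (same 2.36 points). The change SD is 4.17·√(1 + k² − 2ρk), and the ANCOVA SD is 4.17·√(1 − ρ²).

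| k | ρ | t test on change | ANCOVA |
|---|---|---|---|
| 1 | 0.3 | 65.8% | 83.6% |
| 1 | 0.5 | 80.0% | 89.9% |
| 1 | 0.7 | 95.1% | 97.5% |
| 0.5 | 0.3 | 82.0% | 83.6% |
| 0.5 | 0.5 | 89.9% | 89.9% |
| 0.5 | 0.7 | 96.5% | 97.5% |

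**5. Simulation check** (20,000 trials per setting, k = 1, 4.17 as the SD of change). Power of the t test against ANCOVA was 80.1% vs 93.4% at ρ = 0.3, 80.3% vs 89.9% at 0.5 and 80.2% vs 85.7% at 0.7. Type I error at ρ = 0.3 was 5.0% and 5.1%, so both tests hold their level.

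**The case against.** The strongest reply is that nothing here is broken. The t test is valid under randomization, and the trial calls itself an exploratory pilot that relies mainly on descriptive summaries. That limits the weight of the point and makes it an improvement rather than a correction. It does not remove the point, because the plan still sets a significance threshold and a power claim for ISSI.

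Second, the gain may be nil. Baseline comes before or around stenting and follow-up is with a stent in place, so equal SDs are not something the design suggests. With a baseline SD half the follow-up SD, the gain is 0 to 3 power points for ρ between 0.3 and 0.7. This stands, and no single figure should be quoted.

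Third, the cost is not exactly one degree of freedom. Chance baseline imbalance adds about 1% to the ANCOVA variance at 100 subjects. At k = ρ = 0.5, power is then 79.6% against 80.0% for the t test. This is correct but negligible.

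Fourth, no power or half-width can be given for VAS, and the gain over the split-plot ANOVA is not quantified. Both remarks stand. That ANOVA still names no baseline covariate.

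Fifth, percent change, listed alongside chi-square tests, could mean the percentage of subjects who changed, which is defined at a baseline of 0. The text is ambiguous, so that side issue is conditional.

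**Conclusion.** The concern holds as a recommended improvement. The planned analysis of ISSI and VAS leaves unused a covariate that is already collected. Apart from the small finite-sample cost, adjustment cannot lose precision.

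The gain ranges from none to substantial and cannot be determined from the documents. Over the assumed grid (ρ 0.2 to 0.7, k 0.5 to 1.25) the change score has 1.00 to 2.15 times the variance of ANCOVA. Read as the SD of change with equal SDs, the stated 4.17 gives a rise from 80% power to between 86% and 94% for ρ from 0.7 down to 0.3. Every ρ, every k and the 2.36-point difference is an assumption or a back-calculation. The planned t test is not invalid.

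**What to change.** For ISSI and VAS scored as continuous, replace the change-score t test at week 1 and week 2, the follow-up times named in the endpoints, with ANCOVA: follow-up score on treatment group, with the subject's own baseline score as covariate. Define baseline as the score recorded before randomization, which Study Methods places after the operation. Report the adjusted mean difference with its 95% confidence interval.

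Keep the change-score t test as a sensitivity analysis at most. Either label the split-plot ANOVA supportive, or fit it to post-baseline visits with baseline as covariate. Drop within-subject percent change as a tested outcome; if something else was meant by percent change, define it. The chi-squared tests for ordinal scoring and the voiding diary analysis are not affected.

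The cost is SAP wording, one residual degree of freedom and the roughly 1% variance inflation noted above. No extra data or visits are needed. The change should be made before unblinding.

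### Where a score is analysed in three or more ordered categories, the planned chi-squared test ignores the order and loses power; the diary counts need one fully specified primary test

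*Combined protocol and SAP*

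**What the plan says.** The document has one analysis section, Statistical Analyses. Its Primary Endpoints bullet compares change from baseline in ISSI and the voiding diaries between arms by "an independent t test for continuous scoring and a chi-squared test for ordinal scoring". The Exploratory Endpoints bullet repeats the same pair of tests for VAS and for PGI-S. Neither bullet says which measures are scored as ordinal or how many categories they have, and no trend, rank or proportional-odds version is named.

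The Primary Endpoints bullet then adds that inference on changes in micturitions and incontinence episodes per 24 hours "will be performed using a stratified rank analysis to compare to baseline and as a covariance for each treatment". It names no stratification factor.

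Three other statements in the document bear on the point:

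- The same section plans a split-plot repeated-measures ANOVA for ISSI, VAS and PGI-S. It does not cover the diary counts.
- The power statement is for ISSI, "using an estimated SD for each study group of 4.17" and "a sample size of 50 in each study group".
- Randomization Schema describes allocation from a plain table of random numbers, without strata. Statistical Analyses mentions cohorts for summary tables only and does not define them.

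**The concern.** The endpoints are directional: the trial looks for improvement. A Pearson chi-squared test on a two-by-k table gives the same result however the k categories are shuffled. It therefore tests for any difference in distribution, not for a shift toward milder symptoms, and spreads its sensitivity over k − 1 degrees of freedom. With 50 patients per arm there is little power to spare.

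For the two diary counts the difficulty is specification. The bullet can be read as giving them both the t/chi-squared pair and a rank analysis. The rank analysis could be a comparison with baseline, a rank analysis of covariance or a stratified rank-sum test. Two analysts could reach different p-values on a primary endpoint, and the choice could be made after the data are seen.

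**Working it through.** **Inputs from the document.** 50 per arm ("100 subjects will be equally randomized into 1 of 2 study groups"), "significance level (alpha) of 0.05 (two-tailed"), SD 4.17 for ISSI, and the chi-squared test for ordinal scores. The number of ordinal categories is not stated, so 4 and 7 levels are assumed below, and 2 to 10 in the second model.

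**The plan's own power figure.** The plan says the sample "has an 80% power to detect an ISSI difference of 25% between the two groups". The detectable difference is (1.96 + 0.84) × 4.17 × √(2/50) ≈ 2.34 points, or 0.56 SD. This equals 25% only if the reference ISSI mean is about 2.34 / 0.25 ≈ 9.35. The document gives no such mean, so the 80% can be neither confirmed nor refuted. What matters here is that the calculation uses an SD: it treats ISSI as continuous and says nothing about the power of a chi-squared test.

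**Proportional-odds shift.** Assumed control proportions are 0.15/0.35/0.35/0.15 (4 levels) and 0.05/0.10/0.20/0.30/0.20/0.10/0.05 (7 levels). The treated arm has its cumulative odds of a milder category multiplied by the odds ratio. Simulated power at 50 per arm, two-sided 0.05:

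| Levels | Odds ratio | Chi-squared | Wilcoxon | t test on category scores | Chi-squared minus Wilcoxon (points) |
|---|---|---|---|---|---|
| 4 | 2.0 | 32% | 46% | 46% | −14 |
| 4 | 2.5 | 51% | 69% | 69% | −18 |
| 4 | 3.0 | 70% | 84% | 84% | −14 |
| 7 | 2.5 | 40% | 73% | 71% | −33 |

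Simulation error is about 2 points. Type I error is about 5% or slightly below for chi-squared and Wilcoxon.

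**Check by formula (4 levels, odds ratio 2.5).** The control cumulative proportions 0.15, 0.50, 0.85 become 0.306, 0.714, 0.934, so the treated proportions are 0.306/0.408/0.220/0.066. The chi-squared noncentrality is n Σ(p0 − p1)²/(p0 + p1) = 50 × (0.0534 + 0.0044 + 0.0297 + 0.0327) ≈ 6.0. On 3 degrees of freedom that gives power of about 52%, in line with the simulated 51%.

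**Second model.** A normal shift of 0.56 SD, cut into k equally likely categories, 50 per arm:

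| k | Chi-squared | Wilcoxon |
|---|---|---|
| 2 | 60% | 60% |
| 3 | 58% | 69% |
| 4 | 56% | 73% |
| 7 | 44% | 75% |
| 10 | 37% | 76% |

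Under this model 80% power needs about 82 per arm by chi-squared against 60 by Wilcoxon with 4 categories, and 96 against 58 with 7. With k = 2 the tests are equivalent.

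**The stratum.** There is nothing to compute. The analysis section names no stratum, the randomisation has none, and the cohorts mentioned for summaries are undefined.

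**The case against.** The strongest reply is that the power loss barely reaches the primary analysis. A reader might infer from the table that the trial's main ISSI comparison loses 14 to 33 points of power. The document does not support that reading:

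- The ISSI power statement uses an SD, and the VAS is analysed as a total on a 10 point scale. Both point to the t test named in the same sentence.
- In the scenarios above, a t test on the category scores recovers essentially all of the loss.
- The split-plot ANOVA, which also uses the order, is planned for ISSI, VAS and PGI-S.
- Chi-squared may be meant partly for proportions, since the section's general paragraph pairs chi-squared and t tests with percent change and mean change. On a two-category outcome it loses nothing.

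All of this stands and limits the point. It does not remove it: the plan still prescribes chi-squared for any ordinal score and gives no rule for when a score is ordinal.

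On the diary counts, the second sentence of the Primary Endpoints bullet can be read as the specific rule that overrides the first, since the diary also records urgency. That makes the conflict smaller, but the rank analysis itself remains undefined.

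A reader might also infer that a stratified analysis is impossible because randomisation is unstratified. That does not follow: strata may be defined from baseline data. Nor does the document point to sex as the missing stratum. The phrase "stratified rank analysis to compare to baseline and as a covariance for each treatment" suggests adjustment for baseline, which a test stratified by sex alone would drop.

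Finally, this is an exploratory pilot that relies mainly on descriptive summaries. That lowers the stakes, but the plan also sets inferential tests and a 0.05 threshold.

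**Conclusion.** The point holds, with limited reach. For a score analysed in three or more ordered categories, the named test is inefficient against a shift. At 50 per arm the loss is about 14 to 18 points of power with 4 levels and about 33 points with 7 levels at an odds ratio of 2.5. These sizes rest on assumed category proportions, an assumed number of levels and a proportional-odds shift; the normal-shift model shows the same pattern, and at two categories the loss is nil.

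It mainly concerns the PGI-S comparison, an exploratory endpoint that also has the split-plot ANOVA, and any other score that is categorised. It is not a finding that the ISSI or VAS analysis is underpowered by these amounts. For the two diary counts, the missing stratum and the unclear choice of test are gaps in specification, with no figure attached.

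**What to change.** 1. State for each measure whether it is analysed as continuous or ordinal.
2. For ordinal scores, replace the chi-squared test with a Wilcoxon rank-sum test, or with a proportional-odds model adjusted for baseline category. Keep chi-squared for two-category or unordered outcomes.
3. For micturitions and for incontinence episodes per 24 hours, name one primary test: a rank analysis of covariance on the baseline value, or a rank test stratified by stated baseline categories. It replaces both the t/chi-squared pair and the present stratified rank wording for these counts.
4. Define the baseline diary value in the same edit. Study Methods obtains it 14 days after stent removal, and the schedule of assessments shows no diary at the baseline visit. A value recorded after randomisation is not a true baseline covariate. The planned change from baseline already depends on it, so the new test does not create this problem, but the SAP must settle it.

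The cost is SAP wording: no added patients or visits are needed to change the tests. A proportional-odds model brings a modelling assumption that the Wilcoxon test does not need.
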